## **5.8 Follow-up**

Participants will be followed up daily during the hospital admission (see clinical evaluations, section 6.1.2). If participants are discharged before day 7, they will be phoned on day 7 to ascertain outcome (alive, died, re-admitted) and asked to come to the clinic when 28 days old. If participants are discharged between day 7 and day 28, they will be asked to return to the routine KMC unit clinic on day 28 of life where they will have repeat swab samples (skin, rectal) taken, undergo anthropometry and document feeding practices and outcome (alive; dead). If 28 days falls on a weekend, they will be asked to come on the closest working day (E.g. if a Saturday, come on Friday, if day 28 is Sunday, to come on Monday) with a window period of 5 days (28 days +/- 5 days). If participants do not attend follow-up clinic a telephone call will be made the same day to ascertain outcome and feeding practices and to arrange follow-up as soon as possible. Routine follow-up out with the planned study follow-ups will be provided by the study site staff according to standard practice and clinical need of the baby.

## **5.9 Other study procedures**

In-order to conduct a process evaluation of the study and intervention on study outcomes, additional health systems and clinical data will be prospectively collected. This will include:

Protocol #: 1

---

1. Admission data for all neonatal unit admissions to observe changes in bed capacity; referral patterns; proportion of preterm/LBW admissions and mortality rates, etc
2. Monthly surveys of staffing; equipment; drug availability and infra-structure
3. 6 monthly neonatal quality of care survey, including progress monitoring of KMC provision/services and audit of KMC unit data 6 monthly environmental surveillance of neonatal unit and KMC unit
4. Annual documentation of national health delivery, finances and staffing levels, including national survey of neonatal/KMC provision. This will also include documentation of the costs involved in providing early KMC, to enable a future economic analysis of the intervention.

## **5.10 Final study visit**

The final study visit will be at the hospital KMC unit clinic at 28 days of age, as described in section 5.4.6.

# **6 STUDY EVALUATIONS**

## **6.1 Clinical evaluations**

### **6.1.1 Evaluations during first 24h of intervention**

All subjects will have continuous cardio-respiratory monitoring with a Nonin 2500A pulse oximeter for minimum 24h after intervention/control procedures begin and continued until the subject is stable (definitions, page 10).

Manual auxiliary temperature will be taken 6hrly for the first 24h. The subjects will be reviewed every 6h for manual recording of the respiratory rate and breathing pattern and reviewed at least once by the study clinician during the initial 24h period. An adapted SCRAP score will be calculated post-hoc to quantify cardio-respiratory stability (Appendix 3). Blood sugar measurements will be measured every 6h, unless  $<2.6$  mmol/l in which case it will be measured 1hrly until 2 or more consecutive readings are in normal range (2.6 – 6.9 mmol/l).

### **6.1.2 Evaluations from 24h to hospital discharge**

Starting at 48h of study participation, all subjects will be followed up daily until admission to the KMC unit and then weekly on day 7, 14, 21, 28 of life during the KMC unit stay. If a baby requires re-admission to the neonatal unit the reviews will restart every day until KMC unit admission or discharge from the neonatal unit. The following actions will be done using study specific equipment:

- a. Daily review with the following trial assessments documented:
  - Date and time of starting breast milk feeding and date that full breast milk feeding is established
  - Date and time of starting breastfeeding
  - Daily recording of IV fluid volumes, drip rates and medications given
  - Daily measurement of vital signs (heart rate, respiratory rate, oxygen saturation, temperature, blood glucose)
  - Compliance with the standardised management protocol and discussion of any deviations with study site medical team
- Documentation of details about skin-to-skin contact:
  - Date and time of skin-to-skin contact initiation
  - Duration of skin-to-skin contact/day
  - Person providing skin-to-skin contact

Protocol #: 1

- Whether skin-to-skin contact is temporarily discontinued and date/time of this event
- Documentation of patient flow through the ward Identification and documentation of any change in clinical condition warranting temporary cessation of intervention and date/time of temporary cessation
- Identification of any SAE

b. Weighed on day 5, then daily until discharge(to be done at an appropriate time in collaboration with study site staff and clustered with other procedures, E.g. changing of nappies)

c. OFC and length to be measured weekly using study equipment

d. Neonatal skin and rectal swab sample to be taken on days 7 and 28 if still an inpatient or attending outpatient clinic

Study site staff will be responsible for the ongoing medical and nursing management of the neonate according to the standardised management protocol with input from the study team if requested.

#### **6.1.3 Evaluations in event of clinical deterioration**

Study site staff will be given guidance and training on recognition of signs of severe illness according to adapted PSBI criteria (figure 3) and asked to inform research personnel if a baby fulfils the screening criteria. Research personnel (research nurses or clinician) will then examine the baby as soon as possible, for the presence of any signs of infection (figure 4). The participant will also be assessed for signs of severe illness and infection during the daily in-patient review. If the subject meets criteria for suspected late-onset infection they will have blood +/- CSF cultures taken as soon as possible but not to delay antibiotic administration (section 5.3.2). Once samples have been taken, management will be directed by the study site team in accordance with the standardised management protocol and the research clinician will complete the appropriate safety monitoring documentation. The study personnel will also assess if the baby meets criteria for temporary withdrawal from the intervention arm.

Figure 3. Screening criteria for severe illness

Hospital staff to inform study team as soon as possible if any of the following are present:

(adapted PSBI criteria)

- Refusal to feed / abdominal distension or pre-feed gastric aspirates > 50% of feed volume
- Lethargic (not moving or moving with stimulation only)
- Respiratory rate >80 bpm or severe chest wall indrawing or new oxygen/CPAP requirement
- Apnoea\*
- Auxillary temp >37.5
- Auxillary temp <35.5 (after 1h of observed skin-to-skin contact)
- Convulsions

Figure 4. Criteria for investigation of suspected late-onset infection

Take blood +/- CSF culture if clinical deterioration at  $\geq 72$ h of age and has 1 of:

- Jaundice
- Apnoea\*
- Hepatomegaly
- Pallor
- Lethargy or movement only when stimulated

Protocol #: 1

---

\*Spontaneous apnoea with no identifiable reason. (E.g. not associated with milk aspiration, severe respiratory distress or end stage respiratory failure)

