#### 4.2.1. Inclusion criteria

Neonates:

- New admission to the neonatal unit at EFSTH during the study period
- Admission weight less than 2000g
- Age 1 – 24h at time screening begins
- Alive at time of enrolment
- Singleton or completed twin birth admission
- Written informed consent provided by a parent/caregiver

Mother/caregiver:

- Paired neonate is enrolled in the study
- Is available and willing to provide continuous skin-to-skin contact
- Provides written informed consent

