#### 4.2.2 Exclusion criteria

*Neonatal recruitment*

- Congenital malformation which is incompatible with life or requires immediate surgical correction
- Severe jaundice needing immediate management
- Seizures
- Clinically stable as assessed over a pre-defined period of cardio-respiratory monitoring (see definitions, page 10)
- Severely unstable as assessed over a pre-defined period of cardio-respiratory monitoring (see definitions, page 10)
- Completed triplet admission
- Mother and/or neonate already enrolled into another MRCG study at time of hospital admission
- No study bed available

*Neonatal rectal swabs (at all time points):*

- Imperforate anus
- Gastrointestinal surgery since birth
- Diarrhoea or watery stool within 24h of swab

*Neonatal skin swabs (at all time points):*

- Topical antibiotic or topical steroid used on neonatal skin since birth or within preceding 7 days
- Multiple blisters, pustules, boils, abscesses, erosions or ulcers on the scalp, face, neck, arms, forearms or hands
- A single blister, pustule, boil, abscess, erosion, ulcer, scab, cut, crack or pink/hyperpigmented patch or plaque at or within 4 cm of the sampling site

*Maternal recto-vaginal swab*

- Known HIV infection
- Major gastro-intestinal surgery within the last 5 years
- Diarrhoea or constipation within the preceding 24h

Protocol #: 1

*Maternal/caregiver skin swab*

- Known HIV infection
- Used topical antibiotic or steroid on skin within 4cm of sampling site in last 7d
- Generalised skin disorder (eczema, psoriasis, scabies, multiple blisters, pustules, boils or abscesses)
- A single blister, pustule, boil, abscess, erosion, ulcer, scab, cut, crack or pink/hyperpigmented patch or plaque at or within 4 cm of the sampling site

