### **5.7.3 Control arm**

Babies allocated to the control arm will be placed in an incubator or under a radiant heater, as per standard management at the study site. They will wear a hat and be wrapped as per standard care. Oxygen will be provided from an oxygen concentrator and IV fluids securely attached to the IV cannula and drip rate calculated, as in the intervention arm. The pulse oximeter will be placed inside the incubator or next to the radiant heater. The parent/caregiver will be able to touch the baby, if requested, but will not provide any skin-to-skin contact until he/she meets stability criteria (definitions, page 10) and is >24h since hospital admission, in keeping with current standard care practices at the study site. The baby will initially receive intermittent KMC (60 minutes after feeds) with the parent/caregiver in a chair next to the incubator or radiant heater in the study area. Once fully stable (definitions, page 10) and not requiring oxygen or IV fluids, the baby will be transferred to the KMC Unit to start continuous KMC.

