## APPENDIX I. SCHEDULE OF RECRUITMENT ACTIVITIES

[figure not shown]
Activity	Tasks/method	Staff member	Documentation	Estimated time *
Identify potential participants	Screen all new admissions to EFSTH NNU to identify those with weight <2000g	MRC research nurse EFSTH nurse	Admission log	5 minutes
Sensitisation	Inform available parents/caregivers of potential participants about the study and screening procedures	MRC research nurse	eCRF	10 minutes
Screening for clinical eligibility	
 
✓ Check age from source documents
 
✓ Weigh on study scale
 
✓ Examination
 
✓ Continuous pulse oximetry for 3h and manual recording of RR and breathing over 10 minute period at 00:00 & 02:50
 
✓ Take temperature / blood glucose to aid clinical management
 
	MRC research nurse	
 
1. Screening log
 
2. Eligibility checklist with criteria
 
3. Screening Clinical Assessment Form
 
	20 minutes  10 minutes OR 2h 50 minutes
Informed consent	Informed consent for eligible babies: 
 
- Consent for baby to participate in RCT
 
- Consent to providing intervention if randomised to that arm
 
	MRC research nurse/research Clinician	Information sheets & consent forms	40 minutes – 3h
Enrolment	Allocate unique study ID number to neonate and parent/caregiver	MRC research nurse	Enrolment logs	5 minutes
Collection of baseline data	✓ Auxiliary temperature	MRC research nurse	1. Clinical assessment form	30 minutes
	✓ Blood glucose		2. Biological samples log sheet	10 – 30 minutes
	✓ Head circumference & length measurement		3. Transport log sheet	
	✓ Neonatal rectal, skin, & nasal swabs			
	✓ Maternal/caregiver paired swab samples (within 24h)		eCRF	60 minutes (as soon as possible)
Randomisation & allocation	Randomised & allocated to intervention or control arm	Research clinician	Randomisation log	10 minutes

\* Screening, and enrolment activities are estimated to take between 2hr 20 minutes and 6h 10 minutes to complete (not including collection of socio-demographic data). If the informed consent process is delayed for any reason, this may be extended but the baby will be ineligible if no consent within 24h of admission.

Protocol #: 1

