### *3.1.3. Control procedures*

Participants were managed in an incubator or under a radiant heater, naked except for a woollen hat and nappy or wrapped in a cloth. The parent/caregiver could touch, hold, and feed the neonate as per standard practice but KMC was not provided until stability criteria were met and at greater than 24h since hospital admission. Participants received intermittent KMC in the trial area and continuous KMC was started after transfer to the adjacent KMC unit.

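### Minor wording fix: the low-temperature call trigger in Figure 3 of Protocol 6.1.3 requires prior skin-to-skin contact, so one sign is ascertained unevenly between arms

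*Protocol*

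**What the plan says.** Protocol 6.1.3 contains a Figure 3 listing seven signs of severe illness. (The protocol has another Figure 3, on consent, which is not meant here.) Hospital staff are to tell the study team when any one sign is present. There is one list, with no version by arm. The high-temperature line, above 37.5, carries no condition. The low-temperature line does: "Auxillary temp <35.5 (after 1h of observed skin-to-skin contact"). After a call, research personnel "will then examine the baby as soon as possible, for the presence of any signs of infection".

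The contact rules differ by arm:

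- **Control:** the parent or caregiver "will not provide any skin-to-skin contact until he/she meets stability criteria" and more than 24 hours have passed since admission (Protocol 5.7.3). The SAP repeats this in 3.1.3: "KMC was not provided until stability criteria were met and at greater than 24h since hospital admission".
- **Intervention:** contact starts within 24 hours of admission, with a target above 18 hours a day (SAP 3.1.2).
- **Both arms:** Protocol 9.1.2 applies the same criteria for starting intermittent and continuous contact to control babies and to intervention babies returning after withdrawal. They include being stable, off oxygen, not on phototherapy for severe jaundice, and having a willing caregiver.

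Stable babies are not enrolled. The exclusion criteria in Protocol 4.2.2 list "Clinically stable as assessed over a pre-defined period of cardio-respiratory monitoring".

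**The concern.** A prompt used in both arms should depend on the baby's condition, not on allocation. Here the condition attached to one sign is itself the treatment being compared. A cold control baby in an incubator gives staff no reason under this line to call. An equally cold intervention baby, an hour into contact, does.

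Two uses of the list make this more than a matter of style. SAP 3.6 names ad-hoc reviews after clinical deterioration among the assessments behind the suspected-infection outcome, and Figure 3 calls lead to such reviews. Protocol 8.2 counts deterioration under the same adapted PSBI criteria as an adverse event. Staff know the allocation, and thermal control is one of the pathways by which the intervention is expected to work (Protocol 1.2, SAP 2.2). The affected sign is therefore one on which the arms are expected to differ.

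**Working it through.** No calculation applies. The check sets the Figure 3 line against the contact rules and then follows what a call leads to.

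**Step 1: who can meet the line.** I take the hour of contact to be the hour before the reading, which is the natural sense of the parenthesis. Reading A takes the line as written. Reading B takes the parenthesis to qualify only babies who are in contact.

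| Baby's situation | Reading A | Reading B |
|---|---|---|
| Control, contact not yet allowed | cannot meet it | meets it at once |
| Control, after 1 hour of contact | can meet it | can meet it |
| Intervention, first hour of contact | cannot meet it | cannot meet it |
| Intervention, after 1 hour of contact | can meet it | can meet it |
| Intervention, temporarily withdrawn | cannot meet it | meets it at once |

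Every control baby starts in the first row, because stable babies are excluded at entry and contact also waits for the 24-hour mark. A control baby leaves that row when the 5.7.3 and 9.1.2 criteria are met. Intermittent sessions then last 60 minutes, so the condition can be satisfied. The dependence thus runs through contact status, which follows allocation mainly in the early part of the stay. Neither reading treats the arms alike.

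**Step 2: how long this lasts.** The documents do not say. The 24-hour clause is only one of the bars to contact. The others, chiefly stability and the remaining 9.1.2 criteria, have no stated duration.

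**Step 3: what a call can change.**

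- *Mortality, 24-hour hypothermia, SAE comparison:* none uses the trigger. Temperature is taken 6-hourly in both arms over the first 24 hours (Protocol 6.1.1), and SAP 6.5 gives by-arm counts for SAEs, none of which is defined by low temperature.
- *Suspected infection:* the definition and Figure 4 rest on five signs (pallor, lethargy, jaundice, apnoea, hepatomegaly), with a 72-hour age threshold. Temperature is not among them. Lethargy and apnoea are Figure 3 signs in their own right and trigger a call in either arm. A low-temperature call can matter only by prompting an examination, after the threshold, that finds pallor, jaundice or hepatomegaly that would otherwise be missed or found later. By then the babies who cannot meet the line are control babies still not eligible for contact and withdrawn intervention babies.
- *Adverse events:* if the list is applied literally, recording of this sign under the adapted PSBI category can be uneven. SAP 6.5 plans no by-arm test of that category.

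**Step 4: what covers the gap.** Protocol 5.8, 6.1.3 and 8.5 provide for daily review of in-patients by study personnel in both arms. Section 6.1.2 specifies the daily trial assessments, including temperature, from 48 hours of participation until transfer to the KMC unit, where its reviews become weekly. Pulse oximetry runs in both arms until the baby is stable (Protocol 8.1). The other six Figure 3 signs carry no contact condition.

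**The case against.** The best defence is that no one would apply the line literally. On that view the parenthesis tells staff to recheck a cold baby after an hour of warming by contact, and a very cold control baby would be reported anyway. Staff were to receive guidance and training on these criteria, and neither that material nor the standardised management protocol is among the documents. How the line was used cannot be judged from the text. This is fair, and it is why the point is confined to the wording. It does not remove the imbalance: under that reading control babies are reported at once and intervention babies only after an hour.

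The defence can add that Protocol 8.2 has other adverse-event categories, such as any deterioration needing a change in management, that would capture a cold control baby without Figure 3. That also stands, and it limits the loss.

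A reader might go further and infer that cold control babies went untreated, or that the research team could remain unaware of them for a day or more. The documents do not support either. Site staff direct care in both arms without waiting for the call (Protocol 6.1.2 and 8.1), and daily review is stated in several places. A reader might also infer that the infection comparison is biased in a known direction. The direction depends on which reading staff used, and the route to that outcome is indirect.

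**Conclusion.** The point holds as a low-priority correction to one of seven lines. As written, the low-temperature prompt cannot be met by a baby out of skin-to-skin contact, and contact is what the trial randomises. One sign is therefore ascertained unevenly between arms, with possible small consequences for examinations that feed the suspected-infection outcome and for adverse-event recording.

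The size is unknown and probably small. No frequency of temperatures below 35.5 is given, nor any time to stability, so no count of missed or extra calls can be derived. The conclusion assumes that Figure 3 was the list staff worked from and that no arm-specific version existed elsewhere. It does not extend to the primary outcome, the 24-hour hypothermia outcome or the SAE comparison, and it does not show bias in the infection result.

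**What to change.** Reword the one line so that it refers to warming by any method, for example: *below 35.5 °C after 1 hour of observed warming by skin-to-skin contact, incubator or radiant heater*. The sponsor's clinicians should settle the final wording. This keeps the apparent purpose of the one-hour condition and also covers intervention babies who are temporarily out of contact. Change the staff training sheet to match. No SAP change is needed, and no endpoint, sample size or significance level is affected.

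The cost is one line of text, one training sheet and somewhat more calls for control babies. SAP 3.1 dates the trial from May 2018 to April 2020, so the correction serves the protocol text and any reuse of it. It cannot alter data already collected.

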#### **6.1.4 Procedures at time of discharge or death**

The subject will be discharged according to KMC unit discharge criteria by study staff.

The following will be documented on the eCRF within 24h of discharge or death:

- Date and time of discharge or death; Cause of death; Most recent weight before death/discharge; Details of feeding at time of death/discharge.

At time of discharge, the parent/caregiver will be given pictorial information about danger signs and instructed to contact the study team or seek medical help if the baby becomes unwell before 28d of age. They will be provided with the study team contact numbers and a study participant ID card.

#### **6.1.5 Procedures at follow-up**

At the day 28 follow up they will be seen by study personnel, have repeat swab samples taken, undergo anthropometry (measurement of weight, OFC and length) and be asked about general health and feeding practices.

### **6.2 Microbiological evaluations**

The following is a summary table of all biological samples to be taken during the study:

Table 1. Summary of all biological samples to be taken during clinical study

Source	Type of sample	Site of sampling	Timing	Purpose
Neonate	Swab samples	Rectal Skin	D0, 7, 28	Storage for future ESBL- gram-negative bacilli carriage & molecular analysis
	Blood culture	Peripheral venous blood	If suspected LOS	To confirm LOS & storage for future molecular analysis
	CSF culture	Lumbar puncture	If suspected LOS	To confirm LOS & storage for future molecular analysis
Caregiver (if mother not immediately available)	Swab sample	Skin	Before starting KMC	Storage for future molecular analysis
Mother	Swab sample	Recto-vaginal Skin	Before starting KMC	Storage for future ESBL- gram-negative bacilli carriage & molecular analysis
Environment	Swab samples	Surface swab samples Aliquots of IV fluid and IV antibiotic	6 monthly intervals before and during study period	Identification of outbreaks, gram-negative reservoirs & storage for future molecular analysis

Protocol #: 1

---

### **6.2.1 Collection of swab samples for storage**

Size specific FLOQ swab® will be used and all swabs inserted into Amies transport medium at time of collection.

Neonatal skin swabs will be taken as a composite swab from the xiphisternum and the peri-umbilical area. Rectal swabs will be taken by inserting the swab into the rectum and rotating gently.

Maternal RV swabs will be taken by inserting the swab first into the vagina, then into the rectum and rotating gently. Maternal skin swabs will be taken from the xiphisternum. All procedures will be detailed in the Biological Samples SSP.

